641 Hospitalization admission and discharge dates (pre-transplant and post-transplant).

642 Number of ICU days. Major interventions performed during inpatient hospitalizations

643 **4.7.4. Sample Size and Power Calculations**

644 For comparing hospitalization between LDLT recipients and non-recipients we consider
645 the number of hospital days in one year. Although the analysis will take into account the
646 possibility that some patients may be included in both groups, both pre- and post-LDLT,
647 the power calculations consider a similar but simplified design based on a two-sample t-
648 test (2-sided, $\alpha=0.05$), assuming 300 LDLT recipients and 500 non-recipients. We
649 have no preliminary data on means or standard deviations (s.d.s) for number of hospital
650 days in a year, but assuming a fairly large s.d. of 25 days, we will have 93% power to
651 detect a difference of 5 days (effect size = 0.20 s.d.) between LDLT and non-LDLT
652 groups.

653 **4.7.5. Statistical Analysis**

654 Resource utilization, particularly hospitalization (number of hospitalizations and number
655 of hospital days) will be compared for those with and without LDLT using a repeated
656 measures logistic regression analysis. In addition, a comparison of hospitalization after
657 LDLT versus cadaveric transplant will be made.

658 **5. Human Subjects**

659 **5.1. Protection of Human Subjects**

660 **5.1.1. Institutional Review Board**

661 This data collection and analysis will be performed under Institutional Review Board
662 (IRB) oversight. Prior to the initiation of the study, an IRB approval for study of human
663 subjects will be obtained separately from the IRB of each of the participating transplant

664 centers and the DCC. Revisions to the study protocol and changes in the study design
665 will also be submitted to IRBs for approval prior to implementation.

666

667 Each center will complete an application to their own IRB to allow receipt of the center-
668 specific SRTR-identified data set and the abstraction of additional information from the
669 medical record and release of this identified information to the DCC for analysis. The
670 application will request a waiver of written informed consent for this retrospective
671 project. The DCC will also have in place an IRB approved protocol to complete its
672 responsibilities for the study. The DCC will, in turn, receive identifiable data from the

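### Section 4.7.4 claims 93% power for the hospital-days comparison, but the inputs printed beside it give 78%

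*Protocol*

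**What the plan says.** Protocol section 4.7.4 gives the power for the resource utilization study, whose primary aim is in section 3.7.1. The outcome is "the number of hospital days in one year". The protocol states that "the power calculations consider a similar but simplified design based on a two-sample t"-test, two-sided at alpha 0.05, "assuming 300 LDLT recipients and 500 non-recipients". It says that no preliminary data on means or standard deviations exist, and concludes: "assuming a fairly large s.d. of 25 days, we will have 93% power to" "detect a difference of 5 days (effect size = 0.20 s.d.) between LDLT and non-LDLT" groups.

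The test, its sidedness, the significance level, both group sizes, the difference, the SD, the standardised effect and the resulting power are therefore all stated together.

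**The concern.** The difference, the SD and the effect size agree with one another, since 5/25 = 0.20. The power does not agree with them. A standardised difference of 0.20 with 300 and 500 patients falls a little short of 80% power, not above 90%.

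At stake is what the cohort is said to be able to detect. A reader who accepts 93% would take a non-significant result as fairly strong evidence against a 5-day difference in hospital stay. At the stated inputs the evidence would be clearly weaker. The comparison serves the primary aim of this sub-study. Section 5.1.1 adds that the retrospective results are to inform the planning of the prospective study.

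**Working it through.** **Inputs, all from section 4.7.4**

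- Test: two-sample t, two-sided, alpha = 0.05
- n1 = 300 (LDLT), n2 = 500 (non-LDLT)
- Difference = 5 days, SD = 25 days, effect size d = 5/25 = 0.20
- Stated power: 93%

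**Attempt to reproduce the stated figure**

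Standard error of the difference: SE = SD × √(1/n1 + 1/n2) = 25 × √(1/300 + 1/500) = 1.826 days.

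Standardised signal: 5/1.826 = 2.739. Equivalently, 0.20 × √(300 × 500/800) = 0.20 × 13.69 = 2.739.

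Normal approximation: power = Φ(2.739 − 1.960) = Φ(0.779) = 78.2%.

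Noncentral t, df = 300 + 500 − 2 = 798, noncentrality 2.739: power = 78.1%.

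The stated 93% is not reproduced. The gap is about 15 percentage points.

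**Could another reading of the same design give 93%?** (d = 0.20 throughout)

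| Variant | Power |
|---|---|
| As stated: 300 vs 500, two-sided | 78% |
| 300 vs 500, one-sided 0.05 | 86% |
| 400 vs 400, two-sided | 81% |
| 335 vs 527 (Appendix A totals: 335 received LDLT, 862 − 335 = 527 did not), two-sided | 82% |

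None of these reaches 93%.

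**What would give about 93%?**

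- 300 vs 500 with SD 20 (d = 0.25): SE = 20 × √(1/300 + 1/500) = 1.461, 5/1.461 = 3.423, power 92.8%.
- A one-sample test with n = 300 at d = 0.20: 93.4%.
- A one-sided test with 500 per group at d = 0.20: 93.5%.

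Each conflicts with something the section states. They are numerical matches only; the protocol does not show how 93% arose.

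**What 93% power means at the stated SD**

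- Detectable difference with 300 vs 500 at SD 25: (1.960 + 1.476) × 1.826 = 6.27 days. The noncentral t gives 6.28. This is about 6.3 days, or 0.25 SD.
- Sample size for 5 days at SD 25 and the same 3:5 ratio: non-recipients = (1 + 5/3) × ((1.960 + 1.476)/0.20)² ≈ 787, and recipients = 0.6 × 787 ≈ 472. That is about 1,260 in all, against 800.

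**Check of the method on another calculation in the protocol**

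Section 4.3.4 uses the same test for the fibrosis score: 100 vs 83 patients, difference 0.5, SD 1.0, stated power 91%. The same noncentral t calculation gives 91.8%, which agrees to within a point. The mismatch in 4.7.4 is thus not explained by a different convention for t-test power.

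**The case against.** The best defence is that nothing in the design depends on this number. The cohort consists of every eligible patient in a closed historical period, the 300/500 split comes from feasibility counts, and the main objective of the study is survival. Resource utilization is one of several sub-studies, and section 9 does not list it separately among the expected publications. The protocol also labels the t-test a simplification and the SD an assumption. The analysis planned in section 4.7.5 is a repeated measures logistic regression, so neither 78% nor 93% is the power of that analysis.

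Much of this stands, and it limits the reach of the point:

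- The correction leaves the sample size and the main survival aim untouched.
- The 22% type II error applies to the simplified t-test on hospital days, not to the whole resource aim.
- An SD of 20 is a possible origin of the figure, not an established one.
- The total of about 1,260 only conveys scale, because a closed cohort cannot be enlarged to meet it.

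None of this makes the sentence correct. The 93% is claimed for the simplified test, and the discrepancy lies within that test. Because the SD is an assumption, the sentence is purely conditional: if the SD is 25 days, the power for 5 days is 93%. That conditional statement is false.

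**Conclusion.** The concern holds. With the test, alpha, group sizes, difference and SD stated in section 4.7.4, the power is 78%, not 93%. For that test the type II error is 22% rather than 7%, about three times as large. At the stated SD, 93% power corresponds to a difference of about 6.3 days instead of 5.

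The result uses only the protocol's own inputs and the usual t-test assumption of a common SD. It does not depend on knowing how the printed figure arose, and it makes no claim about the power of the regression analysis that will actually be run.

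**What to change.** Correct the power sentence in section 4.7.4 in one of two ways:

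- keep the 5-day difference and the SD of 25 days, and state 78% power; or
- keep 93% power and the SD of 25 days, and state the detectable difference as about 6.3 days (0.25 SD).

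If an SD of about 20 days was intended, change the SD to 20 and the effect size to 0.25 together, and give a reason for the smaller SD, since the section reports no preliminary data.

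The cost is one sentence. No patients, data items or analyses change. Under either of the first two options the stated sensitivity of the resource comparison becomes less favourable.

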110 To ascertain which data elements collected via the OPTN data collection process can be
111 reliably employed for use in the prospective A2ALL Cohort Study.

112
113 To provide feedback to the SRTR and OPTN on the accuracy and completeness of
114 selected data elements.

115 **3.6. Retrospective Post-surgical Complications Study**

116 **3.6.1. Primary Aim**

117 To determine the rate of the major donor post-operative complications associated with
118 planned right lobe liver donation

119

120 To compare the major recipient post-operative complications after LDLT versus
121 cadaveric transplant.

122 **3.7. Retrospective Resource Utilization Study**

123 **3.7.1. Primary Aim**

124 To compare the resource utilization for patients who proceed to LDLT versus those for
125 whom living donation does not occur and thus proceed toward cadaveric transplant.

126 **4. Investigational Plan**

127 **4.1. Overall Study Design**

128 Most of the specific aims require LDLT recipients and control patients who did not
129 undergo LDLT. However, the identification of these controls and study start time (time
130 0) for following LDLT patients and controls will differ for the various objectives. All, or
131 nearly all, of the LDLT recipients will be included in all analyses, which will simplify
132 chart review. Many of the control patients will also be included in several analyses.
133 LDLT donors will be evaluated for surgical complications.

134

135 For the primary survival and resource utilization objectives, the study entry point is at
136 initial evaluation of a potential living donor that includes history and physical
137 examination at the transplant center. The overall design of the retrospective cohort study
138 is predicated on this definition as the starting point for inclusion in the cohort. In the
139 primary analysis (see below), the mortality of LDLT patients will be compared to
140 mortality of patients who have not yet had LDLT, regardless of subsequent events
141 (cadaveric transplant, death, or removal from waitlist for any other reason). This cohort
142 will include all those evaluated for LDLT transplants from 1/1/98 until 2/28/03. Among
143 the 9 transplant centers in the A2ALL project, approximately 40% of individuals who had
144 a potential living donor identified went on to undergo LDLT, leaving 60% as controls
145 (see Feasibility Study report [Appendix A]). Based on this report, we estimate that

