146 approximately 800 patients were evaluated for LDLT at the 9 A2ALL transplant centers,
147 of which approximately 300 subsequently received LDLT and 500 did not. A subset of
148 this cohort with diagnoses of HCC at entry will also be used.

149

150 Other objectives regarding the post-transplant experience will compare LDLT to
151 contemporaneous cadaveric transplants beginning at the time of transplantation. The
152 analysis will control for center and date of transplantation as well as age, sex, disease
153 (HCC, cholestatic, HCV/HBV, alcoholic, other), and severity of illness (MELD score,
154 OPTN/UNOS status, CTP score). This comparison would involve approximately 300

155 LDLT recipients and approximately 250 cadaveric liver recipients. A subset of this
156 cohort with diagnoses of HCV at entry will also be used.

157

158 Living donor liver transplantation presents unique immunological setting that is
159 determined by three major variables that are different from the cadaveric setting, with the
160 potential to impact on short and long term graft and patient survival. First, regeneration
161 may be associated with different pattern of lymphocyte trafficking in and out the graft
162 resulting in a differential repopulation of the liver with donor cells, and unknown effects
163 on the extent of peripheral chimerism. Second, transplantation of a lobe from a living
164 donor is done under conditions allowing extremely short cold ischemic time (60 vs. 500
165 minutes), a variable that may affect the severity of the inflammatory and immune
166 response. Finally, it is estimated that 40% of LDLT are done in between genetically
167 related individuals, resulting in a potentially more favorable HLA matching.

168

169 Previous single center studies have suggested a reduced rate of rejection after adult to
170 adult LDLT. These observations should be validated by a carefully designed
171 retrospective analysis of rejection rate and severity in AALDLT recipients. The clinical
172 findings will determine the opportunities for appropriate clinical modifications in the
173 immunosuppression protocol for the prospective study, aiming at better outcomes for
174 graft rejection and recurrent disease. Moreover, they will set the stage for hypothesis-
175 driven experimental studies, aiming to determine pattern of immune response and the
176 potential development of favorable induction of tolerance.

177

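### Section 4.7.5 states no covariate adjustment for the primary, non-randomised comparison of hospital use with versus without LDLT, although the survival comparison in the same cohort is adjusted

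*Protocol*

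**What the plan says.** The primary aim in section 3.7.1 is "To compare the resource utilization for patients who proceed to LDLT versus those for" whom living donation does not go ahead. Section 4.1 fixes the starting point: "For the primary survival and resource utilization objectives, the study entry point is at" the first evaluation of a potential living donor.

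Section 4.7.5 holds the whole analysis. Number of hospitalizations and number "of hospital days) will be compared for those with and without LDLT using a repeated" "measures logistic regression analysis. In addition, a comparison of hospitalization after" LDLT versus cadaveric transplant is planned. No covariate, matching or stratification is named anywhere in 4.7.1 to 4.7.5. The one complication noted, in 4.7.4, is that a patient may contribute time both before and after LDLT.

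Section 4.1 does carry an adjustment statement: the "analysis will control for center and date of transplantation as well as age, sex, disease" and severity. It belongs to the paragraph on the post-transplant objectives, which compare LDLT with cadaveric transplant from the date of transplantation.

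The listed data include "Hospitalization admission and discharge dates (pre-transplant and post-transplant") in 4.7.3. For the cohort defined the same way in 4.2, section 4.2.3 lists date of birth, sex, ethnicity, diagnoses, MELD/UNOS/CTP at listing and later changes in these.

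**The concern.** Who receives LDLT is not decided by chance. The reasons for non-donation listed in 4.2.3 include the recipient's condition worsening or improving too far for the procedure, so selection depends partly on severity. Severity plausibly drives hospital days, and so do a center's admission and discharge practices and the calendar period. If these differ between patients with and without LDLT, an analysis without adjustment attributes the difference to LDLT.

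The protocol recognises this for survival: 4.2.5 commits to adjusting for age, gender, race, calendar year of evaluation, etiology, severity, comorbidities and other variables. The resource comparison has the same eligibility definition, time zero and contrast, but makes no such commitment. At stake is whether a difference in hospital days, for which the protocol sizes a target of 5 days, can be read as a consequence of choosing LDLT.

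**Working it through.** **1. Does any other section supply the adjustment?**

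| Comparison | Time zero | Adjustment stated |
|---|---|---|
| Survival, with vs without LDLT (4.2.5) | donor evaluation | yes, covariates named |
| HCV (4.3.2, 4.3.5) | transplant | yes |
| HCC, with vs without LDLT (4.4.1) | donor evaluation | yes, covariates named |
| Recipient complications (4.6.2, 4.6.5) | transplant | yes |
| Resource use, LDLT vs cadaveric (4.7.5, second comparison) | transplant | arguably, through 4.1 |
| Resource use, with vs without LDLT (4.7.5, primary) | donor evaluation | none |

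Section 4.1 places the primary resource objective with primary survival, at donor evaluation, so its list for post-transplant objectives does not reach the last row.

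**2. Do the document's own data show that the groups differ?** Appendix A gives LDLT recipients over candidates.

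- By center: lowest 27/119 = 23% (UCLA); highest 64/119 = 54% (VCU) and 21/39 = 54% (UVA); overall 335/862 = 39%. Pearson chi-square over the nine centers is 60.0 on 8 df (p about 5e-10).
- By year: 27/35 = 77% (1998), 54/99 = 55%, 61/155 = 39%, 99/275 = 36%, 94/298 = 32% (2002). Chi-square is 39.5 on 4 df (p about 5e-8).
- Part of the year trend is follow-up: 124/298 = 42% of the 2002 candidates were still waiting. Leaving out those still waiting gives 27/35 = 77%, 54/96 = 56%, 61/126 = 48%, 99/192 = 52% and 94/174 = 54%. The center difference is therefore the firmer evidence.

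Appendix A has no severity data. That severity differs between the groups is inferred from the listed reasons for non-donation.

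**3. The plan's own precision.** Inputs from 4.7.4: two-sided alpha 0.05, two-sample t-test, difference 5 days, "assuming 300 LDLT recipients and 500 non-recipients", and "days in a year, but assuming a fairly large s.d. of 25 days, we will have 93% power to" detect that difference.

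- SE = 25 × sqrt(1/300 + 1/500) = 1.83 days.
- Noncentrality = 5 / 1.83 = 2.74; power with 798 df = 78%.

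The stated 93% does not reproduce. An SD of 20 days (effect size 0.25) would give it. That is a separate matter; only the SE is carried forward.

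**4. What could a spurious difference do?** With no true effect and a bias of b days, the rejection rate is Φ(b/SE − 1.96) + Φ(−b/SE − 1.96).

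| Assumed bias b (days) | b/SE | False-positive rate |
|---|---|---|
| 1 | 0.55 | 8.5% |
| 2 | 1.10 | about 19% |
| 3 | 1.64 | about 38% |

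The values of b are assumptions; the protocol gives nothing from which to estimate them.

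**5. Would adjustment also raise power?** Let rho be the correlation of the covariates with the outcome, and g the share of group membership that they explain. The noncentrality becomes 2.74 × sqrt(1 − g) / sqrt(1 − rho²). Both rho and g are assumed.

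| g | rho 0.3 | rho 0.4 | rho 0.5 |
|---|---|---|---|
| 0 | 82% | 85% | 88% |
| 10% | 78% | 81% | 85% |
| 20% | 73% | 76% | 81% |

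Unadjusted power is 78%. Confounding means that g is above zero, so a gain cannot be promised and a loss is possible.

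**The case against.** The strongest reply is that 4.7.5 is silent rather than explicitly unadjusted. It names a regression model, which accepts covariates, and covariate lists commonly sit in a statistical analysis plan, which is not at hand here. This stands in part. A reader might infer that the protocol prescribes an unadjusted analysis; it does not say so. But this protocol does commit to adjustment in its own text for its other main between-group comparisons, including the one that shares this cohort and time zero, so the silence is an inconsistency and not merely detail deferred.

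Second, adjustment elsewhere is sometimes generic. Section 4.6.5 leaves it to need, and within 4.4.5 the recurrence difference is a plain confidence interval, although 4.4.1 states adjustment for that study. This is fair, and it supports a short statement rather than a fixed model.

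Third, the repeated-measures design lets recipients contribute time before and after LDLT, so part of the contrast can be within patients. That also stands. It weakens the confounding but does not remove it, because patients who never receive LDLT contribute only to the group without it.

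Fourth, the day-based figures come from a t-test that 4.7.4 itself calls a simplification of the planned analysis, with assumed biases. They show scale only.

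Fifth, covariates measured at or before donor evaluation cannot capture later deterioration or improvement, which is the mechanism that the non-donation reasons suggest. Nor do the listed data guarantee admission dates before donor evaluation; hospital days after that point belong to the outcome. Both limits are accepted.

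**Conclusion.** The point holds for the primary comparison in 4.7.5. No adjustment is stated for a non-randomised contrast, no other section supplies it, and the parallel survival analysis has it. The center imbalance is documented (23% to 54%); the year imbalance (77% to 32%) is partly a follow-up artefact; the severity imbalance is plausible but not quantified. The possible effect on inference, a false-positive rate of about 19% or 38%, rests on an assumed bias of 2 or 3 days and on the simplified t-test with SD 25 days.

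Two stronger conclusions might be drawn, and the document supports neither. One is that adjustment would recover power: that needs covariates unrelated to group, which contradicts the confounding at issue. The other is that baseline adjustment would make the contrast free of confounding: changes after donor evaluation would remain. The LDLT versus cadaveric comparison in 4.7.5 is arguably covered by 4.1 and is not part of this point.

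**What to change.** In 4.7.5, state that the repeated-measures comparison with and without LDLT is adjusted as in 4.2.5: age, sex, race, calendar year of donor evaluation, etiology, and severity by MELD/CTP/UNOS status last recorded at or before donor evaluation. Add center. Where admission dates reach back before donor evaluation, add the prior hospitalization rate over the available look-back, with an indicator where it is missing. This last term is optional, and hospital days after donor evaluation must not enter as a covariate. Add a sentence acknowledging that baseline adjustment does not deal with changes in condition after donor evaluation.

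The cost is a few lines of text and a little more analysis. The main covariates are already abstracted for 4.2, and center is known for every patient. The downside is incomplete or unequal look-back for some patients, which the rate and the indicator handle only approximately.

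### Section 4.7.5 assigns logistic regression to two count outcomes without defining a binary response, so the power stated for a difference in mean hospital days does not carry over to it

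*Protocol*

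**What the plan says.** Section 3.7.1 gives the resource utilization study a single primary aim: to compare resource use between patients who go on to LDLT and those who do not.

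Section 4.7.5 states the analysis in one sentence. It opens "Resource utilization, particularly hospitalization (number of hospitalizations and number" and continues "of hospital days) will be compared for those with and without LDLT using a repeated" "measures logistic regression analysis". No binary response, threshold, time interval or denominator follows. A second sentence adds a comparison of hospitalization after LDLT with that after cadaveric transplant and names no method.

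Section 4.7.4 sets the power target on "the number of hospital days in one year". It acknowledges that a patient may contribute both before and after LDLT, and says that "the power calculations consider a similar but simplified design based on a two-sample t"-test, "assuming 300 LDLT recipients and 500 non-recipients. We" have no preliminary means or standard deviations. With an assumed SD of 25 days it claims 93% power for a 5-day difference.

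Section 4.7.3 collects admission and discharge dates before and after transplant. Section 4.2.3 collects deaths with dates.

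**The concern.** The named model does not fit the named outcomes. How often a patient was admitted and how many days were spent in hospital are counts over a period of follow-up. Logistic regression models the probability of an event and reports odds ratios. To run the analysis as written, someone must choose a binary response that the protocol does not state, and different choices answer different questions.

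Three things are at stake:

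- The sub-study's only aim would be tested on a quantity other than the one it was sized for.
- If the choice were any hospitalization per patient or per segment, the amount of hospital use would be discarded. A short segment or an early death would count the same as a full year free of hospital.
- The response could be chosen after the data are seen, because the protocol does not fix it.

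**Working it through.** **Step 1. The plan's own power figure.** Inputs from 4.7.4: 300 and 500 patients, difference 5 days, SD 25 days (0.20 SD), two-sided alpha 0.05.

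- Expected z = 0.20 × √(300 × 500 / 800) = 0.20 × √187.5 = 2.739.
- Power ≈ Φ(2.739 − 1.960) = Φ(0.779) = 0.782. The exact noncentral t gives 0.781.

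The stated 93% is not reproduced. It fits 0.25 SD (0.928 by noncentral t) rather than 0.20 SD. That is a separate arithmetic error and adds nothing to the present point. The reference value for a mean-difference analysis with the plan's inputs is about 78%.

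**Step 2. Outcome, model and powered quantity side by side.**

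| Section | Outcome | Method | Effect scale |
|---|---|---|---|
| 4.7.4 | Hospital days in one year | Two-sample t-test | Difference in means, 5 days |
| 4.7.5 | Number of hospitalizations; number of hospital days | Repeated measures logistic regression | Odds ratio for an undefined response |
| 4.6.5 | Complications, by type | Logistic for event occurrence, Cox for time to event, ordinary regression for continuous outcomes | Matched to the type |
| 4.3.5 | Fibrosis score | Ordinal logistic, supplemented by ordinary regression | Both, with reasons given |

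Elsewhere the protocol matches model to outcome. Where it wants an ordinal model it says so, and it keeps an analysis on the scale that was powered by t-test. Section 4.7.5 does neither.

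**Step 3. Does the t-test power transfer to a yes/no analysis?** This is an illustration with assumed inputs that are not in the protocol. Yearly days are zero for some patients and gamma-distributed for the rest, with total SD 25, groups of 300 and 500, and 3,000 simulated data sets per row. The yes/no analysis compares the proportions ever hospitalized.

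| Ever hospitalized | Mean days | t-test on days rejects | Yes/no analysis rejects |
|---|---|---|---|
| 60% vs 60% | 20 vs 15 | 77% | 6% |
| 65% vs 60% | 20 vs 15 | 76% | 28% |
| 75% vs 60% | 20 vs 15 | 77% | 99% |
| 75% vs 60% | 20 vs 20 | 5% | 99% |

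In the first three rows the 5-day difference is fixed, yet the yes/no analysis ranges from its type I error level to near certainty. In the last row it rejects although mean days are equal.

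**Step 4. Does it transfer to an in-hospital yes/no model per day?** Let the lower group average m days out of 365 and the other m + 5, with everyone followed for the full year. The odds ratio is [(m + 5)/(360 − m)] ÷ [m/(365 − m)]. With m = 15, as in the illustration, it is (20/345) ÷ (15/350) = 0.05797 ÷ 0.04286 = 1.35. A smaller m gives a larger odds ratio for the same 5 days. Section 4.7.4 says there are no preliminary data on means, so m is unknown and the 5-day target has no fixed counterpart on this scale.

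**Step 5. Is follow-up unequal?** Yes, by design. Patients can contribute segments before and after LDLT. Section 4.2.4 assumes one-year survival of 0.875 with LDLT and considers 0.82 to 0.92 without, so 12.5% and 8% to 18% would die within the year. Section 4.7.5 does not mention time at risk.

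**The case against.** The strongest defence is that the plan means a person-period model. Admission and discharge dates show whether a patient was in hospital on any day, and patients may contribute time before and after LDLT. Repeated-measures logistic regression of in hospital yes/no per day or interval is therefore coherent. Hospital days become a binomial count out of days at risk, and a patient who dies contributes no further rows. New admission yes/no per interval out of hospital could serve similarly for admissions.

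This defeats several stronger conclusions that a reader might infer:

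- *That the counts must be collapsed per patient.* The text does not require it.
- *That early death will look like low use.* This follows only under a per-patient or per-segment yes/no response. The protocol does not say that follow-up time is ignored.
- *That power falls to 59%.* This comes from 2.739 × √(2/π) = 2.185 and Φ(2.185 − 1.96) = Φ(0.225) = 0.59. It assumes a roughly normal outcome cut at its median. The plan proposes no such cut, and yearly hospital days with SD 25 are unlikely to be near normal.

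The defence does not remove the point. The protocol states no per-interval response. That model would give an odds ratio, not mean days or a number of hospitalizations, and Step 4 shows that the powered difference cannot be translated without an unknown mean.

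Two further objections have partial force. The t-test is openly called a simplification, as simpler designs are in 4.2.4 and 4.3.4. But 4.3.5 retains a regression on the mean scale, and 4.7.5 retains nothing on that scale. Also, a log-link count model gives a rate ratio, which is not a difference in days either. That is correct, and the fix must include a contrast in days.

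Interval length, offset and variance estimator could be left to a statistical analysis plan. Naming a model that does not fit the named outcomes is a matter for the protocol.

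**Conclusion.** The point holds in this form: the protocol pairs two count outcomes with a logistic model, defines no response for it, and powers a difference in mean days that the model does not estimate. The power in 4.7.4, whether the stated 93% or the reproducible 78%, describes a t-test on days and not the analysis in 4.7.5.

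The loss has no derivable size. It depends on the binary response chosen and on the distribution of hospital days, and the protocol gives neither. The simulated rejection rates rest on assumed distributions and show only that the two analyses can diverge in either direction.

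The repeated-measures element is sound, because patients can contribute both before and after LDLT.

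The matter should be corrected, but the stakes are limited. It affects the single primary aim of one retrospective sub-study, leaves the mortality objective untouched, and can be repaired with data already planned.

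**What to change.** In 4.7.5, replace the logistic model for the two counts with the following:

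- a repeated-measures count or rate model for number of hospitalizations and for hospital days, for example a negative binomial or quasi-Poisson GEE;
- log person-time at risk as offset, LDLT as a time-varying indicator, and robust variance by patient;
- alongside the rate ratio, the adjusted difference in mean hospital days per person-year, so that the result is on the scale of 4.7.4.

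Keep logistic regression only for an outcome stated to be binary, such as any hospitalization, or in hospital yes/no per interval with the interval given. If the per-interval model was intended as the main analysis, say so and base the power on it.

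The cost is one or two sentences. Admission, discharge and death dates are already to be collected, and the software is standard. There are two small downsides. The result depends on the count-model specification, and one extra step is needed to express it in days. A rate per person-year alive should also be read beside the survival comparison, since it equals days in one year only for patients followed throughout.
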